5.5 Withdrawal of Subjects and Discontinuation of Study

AbbVie may terminate this study prematurely, either in its entirety or at any site. The study will be discontinued or terminated in case of an unacceptable risk, any relevant toxicity, or a negative change in the risk/benefit assessment. This might include the occurrence of AEs with a character, severity or frequency that is new in comparison to the existing risk profile. In addition, data deriving from other clinical trials or toxicological studies which negatively influence the risk/benefit assessment might cause

discontinuation or termination of the study. The investigator may also stop the study at his/her site if he/she has safety concerns. If AbbVie terminates the study for safety reasons, AbbVie will promptly notify the investigator. Advance notice is not required by either party if the study is stopped due to safety concerns.

Subjects can request to be discontinued from participating in the study at any time for any reason. Subjects who discontinue the study prematurely after randomization will not be replaced. The investigator may discontinue any subject's participation at any time for any reason. The AbbVie TA MD may mandate individual subject discontinuation from study drug in case of safety concern.

Subjects must have study drug discontinued immediately if any of the following occur:

- The subject requests withdrawal from the study.
- The investigator believes it is in the best interest of the subject.
- Abnormal laboratory results or AEs that either meet the criteria for discontinuation of study drug as stated in Section 6.2 or rule out safe continuation of the study drug, as determined by the Investigator or the AbbVie TA MD.
- Serious infections (e.g., sepsis) which cannot be adequately controlled by anti-infective treatment or would put the subject at risk with continuation of the study drug.
- Confirmed diagnosis of deep vein thrombosis, pulmonary embolus, or non-cardiac, non-neurologic arterial thrombosis.
- Malignancy, except for localized NMSC or carcinoma in-situ of the cervix.
- Subject develops a gastrointestinal perforation (other than due to appendicitis or mechanical injury).
- The subject becomes pregnant or plans to become pregnant while on study drug.
- Subject is non-compliant with TB prophylaxis (if applicable) or develops active TB at any time during the study.
- Eligibility criteria violation was noted after the subject started study drug, when continuation of the study drug would place the subject at risk.
- Introduction of prohibited medications or dosages when continuation of the study drug would place the subject at risk.
- Subject is significantly non-compliant with study procedures, which would put the subject at risk for continued participation in the trial

Additional requirements related to abnormal laboratory values and selected AEs of special interest are located in Section 6.2 (Toxicity Management).

5.6 Follow-Up After Subject Discontinuation of Study Drug or from Study

Discontinuation of Study Drug and Continuation of Study Participation

To minimize missing data for efficacy and safety assessments, subjects who prematurely discontinue study drug treatment should continue to be followed for all regularly scheduled visits as outlined in the Activity Schedule (Appendix D), unless subjects have decided to discontinue study participation entirely (withdrawal of informed consent). Subjects should be advised on the continued scientific importance of their data even if they discontinue treatment with study drug early. Following discontinuation of study drug, the subject should be treated in accordance with the investigator's best clinical judgment irrespective of whether the subject decides to continue participation in the study.

Premature Discontinuation of Study (Withdrawal of Informed Consent)

If a subject prematurely discontinues study participation (withdrawal of informed consent), the procedures outlined for the Premature Discontinuation visit should be completed as soon as possible, preferably within 2 weeks. In addition, if subject is willing, a 30-day follow-up visit (or phone call if a visit is not possible) after the last dose of study drug may be completed to determine the status of any ongoing AEs/serious adverse events (SAEs) or the occurrence of any new AEs/SAEs.

For subjects to be considered lost to follow-up, reasonable attempts must be made to obtain information on the subject's final status. At a minimum, 2 telephone calls must be made and 1 certified letter must be sent and documented in the subject's source documentation.

In the event a subject withdraws consent from the clinical study, biomarker research will continue unless the subject explicitly requests analysis to be stopped. When AbbVie is informed that samples are withdrawn from research, samples will not be analyzed, no new biomarker analysis data will be collected, and the samples will be destroyed. A subject may withdraw consent for optional biomarker research at any time and remain in the clinical study. Data generated from clinical study and/or optional biomarker research, before subject withdrawal of consent, will remain part of the study results.

5.7 Study Drug

Study drug will be taken orally QD, beginning on Day 1 (Baseline), and should be taken at approximately the same time each day, with or without food. Subjects will be instructed to return all drug containers (even if empty) to the study site personnel at each study visit; study site personnel will document compliance.

Subjects will continue their disease-related concomitant medications therapy as allowed per protocol. AbbVie will not supply any disease-related concomitant medication therapy taken during the course of the study.

AbbVie will supply upadacitinib and matching upadacitinib placebo.

All study drug must be stored at controlled room temperature (15° to 25°C/59° to 77°F). Study drug will be packaged in quantities sufficient to accommodate study design.

Each kit will be labeled per local requirements and this label must remain affixed to the kit. Upon receipt, study drug should be stored as specified on the label and kept in a secure location. Each kit will contain a unique kit number. This kit number is assigned to a subject via interactive response technology (IRT) and encodes the appropriate study drug to be dispensed at the subject's corresponding study visit. All blank spaces on the label will be completed by the site staff prior to dispensing to subjects. Study drug will only be used for the conduct of the study.

The individual study drug information is presented in Table 2.

Table 2. Description of Study Drug

Investigational Product	Mode of Administration	Dosage Form	Strength	Blinded or Open Label	Frequency	Manufacturer
Upadacitinib	Oral	Film-coated tablets	15 mg or 30 mg	Blinded	QD	AbbVie
Placebo for upadacitinib	Oral	Film-coated tablets	Not applicable	Blinded	QD	AbbVie

In cases of state of emergency or pandemic situations, study drug shipment can be made from the study site to the subject if allowed by local regulations. Refer to the Operations Manual for details on direct-to-patient (DTP) shipment of study drug.

5.8 Randomization/Drug Assignment

All subjects will be assigned a unique identification number by the IRT at the Screening Visit. For subjects who rescreen, the screening number assigned by the IRT at the initial Screening Visit should be used. The IRT will assign a randomization number that will encode the subject's treatment group assignment according to the randomization schedule generated by the statistics department at AbbVie.

Subjects will be randomized in a 2:1 ratio to 1 of 2 treatment groups:

- Upadacitinib 30 mg QD (N = 40)
- Placebo (N = 20)

Randomization will be stratified by anti-TNF use prior to baseline and Hurley stage (< III or III).

Subjects in the placebo group will be switched to upadacitinib 15 mg QD at Week 12.

All AbbVie personnel with direct oversight of the conduct and management of the trial (with the exception of AbbVie Drug Supply Management Team), the investigator, study site personnel, and the subject will remain blinded to each subject's treatment through Week 12. Sites and subjects will remain blinded for the duration of the study. In order to maintain the blind, the upadacitinib tablets and placebo tablets provided for the study will be identical in appearance. The IRT will provide access to unblinded subject treatment information in the case of medical emergency.

In the event of a medical situation that requires unblinding of the study drug assignment, the investigator is requested to contact the AbbVie TA MD prior to breaking the blind. However, if an urgent therapeutic intervention is necessary which warrants breaking the blind prior to contacting the AbbVie TA MD, the investigator can directly access the IRT system to break the blind without AbbVie notification or agreement. Unblinding is available in the IRT system via the Unblind Subject transaction, which is available only to the investigator. If the IRT system is unavailable, unblinding may occur by contacting the technical support of the IRT vendor via either phone (preferred) or email ([contact]). For country-specific phone numbers, please see the following website: http://www.endpointclinical.com/helpdesk/.

In the event that the blind is broken before notification to the AbbVie TA MD, we request that the AbbVie TA MD be notified within 24 hours of the blind being broken. The date and reason that the blind was broken must be conveyed to AbbVie and recorded on appropriate eCRF.

5.9 Protocol Deviations

AbbVie does not allow intentional/prospective deviations from the protocol except when necessary to eliminate an immediate hazard to study subjects. The investigator is responsible for complying with all protocol requirements, written instructions, and applicable laws regarding protocol deviations. If a protocol deviation occurs (or is identified), the investigator is responsible for notifying IEC/IRB, regulatory authorities (as applicable), and AbbVie.

In Japan, the investigator will record all protocol deviations in the appropriate medical records at the site.

5.10 Data Monitoring Committee

An external DMC composed of clinicians and statisticians independent of AbbVie and with relevant expertise in their field will review unblinded data from the ongoing study. The DMC is responsible for safeguarding the interests of trial subjects, assessing the safety as well as for monitoring the integrity and interpretability of the trial. The DMC will provide recommendations to the sponsor regarding ongoing trial conduct, or modifications to the trial as described in a separate DMC charter.

In order to maintain sponsor blinding, an external Statistical Data Analysis Center is responsible for performing the analyses described in the DMC charter as well as additional analyses requested by the DMC and facilitating interpretation and answering questions that arise before, during or after DMC review.

The DMC will regularly review unblinded safety data from the ongoing study according to the schedule provided in the DMC Charter, including AEs, laboratory values and vitals sign values.

A separate DMC charter will be prepared outside of the protocol and will further describe the roles and responsibilities of the DMC members, frequency and scope of the data reviews, and expectations for blinded communications.

6 SAFETY CONSIDERATIONS

6.1 Complaints and Adverse Events

Complaints

A complaint is any written, electronic, or oral communication that alleges deficiencies related to the physical characteristics, identity, quality, purity, potency, durability, reliability, safety, effectiveness, or performance of a product/device. Complaints associated with any component of this investigational product must be reported to AbbVie.

Product Complaint

A product complaint is any complaint related to the biologic or drug component of the product or to the medical device component(s).

For a product this may include, but is not limited to, damaged/broken product or packaging, product appearance whose color/markings do not match the labeling, labeling discrepancies/inadequacies in the labeling/instructions (e.g., printing illegible), missing components/product, device not working properly, or packaging issues.

Product complaints concerning the investigational product and/or device must be reported to AbbVie within 24 hours of the study site's knowledge of the event. Product complaints occurring during the study will be followed up to a satisfactory conclusion.

Medical Complaints/Adverse Events and Serious Adverse Events

An AE is defined as any untoward medical occurrence in a subject or clinical investigation subject administered a pharmaceutical product and which does not necessarily have a causal relationship with this treatment. An AE can therefore be any unfavorable and unintended sign (including an abnormal laboratory finding), symptom, or disease temporally associated with the use of a medicinal (investigational) product, whether or not the event is considered causally related to the use of the product.

Such an event can result from use of the drug as stipulated in the protocol or labeling, as well as from "special situations" as accidental or intentional overdose, medication error, occupational or accidental exposure, off-label use, drug abuse, drug misuse, or drug withdrawal, all which must be reported whether associated with an AE or not. Any worsening of a pre-existing condition or illness is considered an AE. Worsening in severity of a reported AE should be reported as a new AE. Laboratory abnormalities and changes in vital signs are considered to be AEs only if they result in discontinuation from the study, necessitate therapeutic medical intervention, meets protocol specific criteria (see Section 6.2 regarding toxicity management), and/or if the investigator considers them to be AEs.

The investigators will monitor each subject for clinical and laboratory evidence of AEs on a routine basis throughout the study. All AEs will be followed to a satisfactory conclusion.

An elective surgery/procedure scheduled to occur during a study will not be considered an AE if the surgery/procedure is being performed for a pre-existing condition and/or the surgery/procedure has

been pre planned prior to study entry. However, if the pre-existing condition deteriorates unexpectedly during the study (e.g., surgery performed earlier than planned), then the deterioration of the condition for which the elective surgery/procedure is being done will be considered an AE.

If an AE, whether associated with study drug or not, meets any of the following criteria, it is to be reported to AbbVie clinical pharmacovigilance or contract research organization (as appropriate) as an SAE within 24 hours of the site being made aware of the serious AE (refer to Section 4.3 of the Operations Manual [Appendix F] for reporting details and contact information):

Death of Subject An event that results in the death of a subject.

Life-Threatening An event that, in the opinion of the investigator, would have

resulted in immediate fatality if medical intervention had not been taken. This does not include an event that would have been fatal if it

had occurred in a more severe form.

Hospitalization or Prolongation of Hospitalization An event that results in an admission to the hospital for any length of time or prolongs the subject's hospital stay. This does not include an emergency room visit or admission to an outpatient facility.

Congenital Anomaly An anomaly detected at or after birth, or any anomaly that results in

fetal loss.

Persistent or Significant Disability/Incapacity

An event that results in a condition that substantially interferes with the activities of daily living of a study subject. Disability is not intended to include experiences of relatively minor medical significance such as headache, nausea, vomiting, diarrhea, influenza, and accidental trauma (e.g., sprained ankle).

Important Medical Event
Requiring Medical or Surgical
Intervention to Prevent
Serious Outcome

An important medical event that may not be immediately lifethreatening or result in death or hospitalization, but based on medical judgment may jeopardize the subject and may require medical or surgical intervention to prevent any of the outcomes listed above (i.e., death of subject, life threatening, hospitalization, prolongation of hospitalization, congenital anomaly, or persistent or significant disability/incapacity). Additionally, any elective or spontaneous abortion or stillbirth is considered an important medical event. Examples of such events include allergic bronchospasm requiring intensive treatment in an emergency room or at home, blood dyscrasias or convulsions that do not result in inpatient hospitalization, or the development of drug dependency or drug abuse.

All AEs reported from the time of study drug administration until 30 days after discontinuation of study drug administration will be collected, whether solicited or spontaneously reported by the subject. In addition, study procedure-related serious and nonserious AEs will be collected from the time the subject signs the study-specific informed consent.

AbbVie will be responsible for Suspected Unexpected Serious Adverse Reactions reporting for the Investigational Medicinal Product in accordance with global and local requirements.

Adverse events will be monitored throughout the study to identify any of special interest that may indicate a trend or risk to subjects.

Adverse Events of Special Interest

The following AEs of special interest will be monitored during the study:

- Serious infections
- Opportunistic infections
- Herpes zoster
- Active TB
- Malignancy (all types)
- Adjudicated gastrointestinal perforations
- Anemia
- Neutropenia
- Lymphopenia
- Renal dysfunction
- Hepatic disorder
- Adjudicated cardiovascular events (e.g., major adverse cardiovascular event [MACE])
- Adjudicated embolic and thrombotic events (non-cardiac, non-central nervous system)

Adverse Event Severity and Relationship to Study Drug

The Investigators will rate the severity of each AE according to the National Cancer Institute Common Terminology Criteria for Adverse Events version 4.03 which can be accessed at: http://ctep.cancer.gov/protocolDevelopment/electronic_applications.

If no grading criteria are provided for the reported event, then the event should be graded as follows:

Mild (Grade 1) Asymptomatic or mild symptoms; clinical or diagnostic observations only;

intervention not indicated

Moderate (Grade 2) Minimal, local, or noninvasive intervention indicated; limiting age

> appropriate instrumental activities of daily living (ADL; instrumental ADL refer to preparing meals, shopping for groceries or clothes, using the

telephone, managing money, etc.)

Severe (Grade 3 - 5)

Grade 3 Severe or medically significant but not immediately life-threatening;

> hospitalization or prolongation of hospitalization indicated; disabling; limiting self care ADL (self care ADL refer to bathing, dressing and undressing, feeding self, using the toilet, taking medications, and not

bedridden)

Grade 4 Life-threatening consequences; urgent intervention indicated

Grade 5 Death related to AE

The Investigator will use the following definitions to assess the relationship of the AE to the use of study drug:

Reasonable After consideration of factors including timing of the event, biologic **Possibility** plausibility, clinical judgment, and potential alternative causes, there is

sufficient evidence (information) to suggest a causal relationship.

No Reasonable

After consideration of factors including timing of the event, biologic **Possibility** plausibility, clinical judgment, and potential alternative causes, there is

insufficient evidence (information) to suggest a causal relationship.

Cardiovascular Adjudication Committee

An independent, external committee of physician experts in cardiovascular adjudication will be utilized to assess potential cardiovascular, embolic, and thrombotic AEs in a blinded manner as defined by the Cardiovascular Adjudication Committee charter.

Gastrointestinal Perforation Adjudication

Two independent, internal adjudicators along with a third potential tie-breaker adjudicator who are gastroenterologists or who have other highly relevant clinical experience will be utilized to assess potential AEs of acute spontaneous gastroinestinal perforation in a blinded manner as defined by the Gastrointestinal Perforation Adjudication Charter.

Pregnancy

While not an AE, pregnancy in a study subject must be reported to AbbVie within 24 hours after the site becomes aware of the pregnancy. If a pregnancy occurs in a study subject, information regarding the pregnancy and the outcome will be collected.

Female subjects should avoid pregnancy throughout the course of the study, starting with the Screening.

Visit through 30 days after the last study drug administration. Results of a positive pregnancy test or confirmation of a pregnancy will be assessed starting with the Screening Visit through the final study visit.

Subjects who become pregnant during the study must be discontinued from study drug treatment (Protocol Section 5.5).

The pregnancy outcome of an elective or spontaneous abortion, stillbirth, or congenital anomaly is considered a SAE and must be reported to AbbVie within 24 hours of the site becoming aware of the event.

6.2 Toxicity Management

The toxicity management of the AEs including AEs of special interest consists of safety monitoring (review of AEs on an ongoing basis, and periodic/ad hoc review of safety issues by an independent Data Monitoring Committee), and, if applicable, interruption of study drug dosing with appropriate clinical management and/or discontinuation of the subjects from study drug. The management of specific AEs and laboratory parameters is described below.

For subjects who discontinue study drug but continue study participation and are on standard of care therapies, these toxicity management requirements do not apply (including alerts from the central laboratory) and any intolerability to standard of care therapies should be managed by the prescribing physician.

Serious Infections: Study drug should be interrupted if a subject develops a serious infection. Study drug may be restarted once the infection has been successfully treated. Subjects who develop active TB must be permanently discontinued from study drug.

Herpes zoster: If a subject develops herpes zoster, consider temporarily interrupting study drug until the episode resolves.

Gastrointestinal Perforation: If a diagnosis of gastrointestinal perforation is confirmed (other than due to appendicitis or mechanical injury), the subject must be permanently discontinued from study drug.

Malignancy: Subjects who develop malignancy other than NMSC or carcinoma in situ of the cervix must be permanently discontinued from study drug. Information including histopathological results should be queried for confirmation of the diagnosis. Periodic skin examination is recommended for subjects who are at increased risk for skin cancer.

Muscle-related symptoms: If a subject experiences symptoms suggestive of myositis or rhabdomyolysis consider checking CPK and aldolase, with clinical management and/or study drug interruption as deemed appropriate by the treating physician.

COVID-19: Interrupt study drug in subjects with a confirmed diagnosis of COVID-19. Consider interrupting study drug in subjects with signs and/or symptoms and suspicion of COVID-19. The COVID-19 eCRF must be completed.

Thrombosis Events: Subjects who develop symptoms of thrombosis should be promptly evaluated and treated appropriately. If the diagnosis of deep vein thrombosis, pulmonary embolus or non-cardiac, non-neurologic arterial thrombosis is confirmed, the subject must be discontinued from study drug.

Management of Select Laboratory Abnormalities: For any given laboratory abnormality, the investigator should assess the subject, apply the standard of care for medical evaluation and treatment following any local guidelines. Specific toxicity management guidelines for abnormal laboratory values are described in Table 3, and may require a supplemental eCRF to be completed. For subjects with ongoing laboratory abnormalities which require data entry into an eCRF, an additional eCRF related to subsequent laboratory abnormalities is only required if the subject has relevant changes in history (e.g., new onset signs or symptoms) or laboratory values which have returned to normal reference range or its Baseline value followed by subsequent laboratory abnormalities meeting toxicity guidelines (considered a new event). All abnormal laboratory tests that are considered clinically significant by the investigator will be followed to a satisfactory resolution. If a repeat test is required per Table 3, the repeat testing is to occur as soon as possible.

 Table 3.
 Specific Toxicity Management Guidelines for Abnormal Laboratory Values

Laboratory Parameter	Toxicity Management Guideline
Hemoglobin	 If hemoglobin < 8 g/dL, interrupt study drug dosing and confirm by repeat testing with a new sample.
	 If hemoglobin decreases ≥ 3.0 g/dL from Baseline without an alternative etiology, interrupt study drug dosing and confirm by repeat testing with new sample.
	 If hemoglobin decreases ≥ 3.0 g/dL from Baseline and an alternative etiology is known or the hemoglobin value remains in the normal reference range, the subject may remain on study drug at the Investigator's discretion.
	 If confirmed, continue to withhold study drug until hemoglobin value returns to normal reference range or its Baseline value.
ANC	 If confirmed < 1000/μL by repeat testing with new sample, interrupt study drug dosing until ANC value returns to normal reference range or its Baseline value.
	 Interrupt study drug if confirmed < 500/μL by repeat testing with new sample. 
If value returns to normal reference range or its Baseline value, restarting study drug is allowed if there is an alternative etiology identified; documentation should include reason that rechallenge is expected to be safe for the subject. Study drug should be discontinued if no alternative etiology can be found. 

Laboratory Parameter	Toxicity Management Guideline
ALC	 If confirmed < 500/μL by repeat testing with new sample, interrupt study drug dosing until ALC returns to normal reference range or its Baseline value.
Total WBC count	 If confirmed < 2000/μL by repeat testing with new sample, interrupt study drug dosing until WBC count returns to normal reference range or its Baseline value.
AST or ALT	 Interrupt study drug if confirmed ALT or AST > 3 × ULN by repeat testing with new sample and either a total bilirubin > 2 × ULN or an international normalized ratio > 1.5.
	 A separate blood sample for international normalized ratio (INR) testing will be needed to measure INR at the time of repeat testing for ALT or AST. A repeat test of INR is not needed for determination if above toxicity management criteria are met.
	 Interrupt study drug if confirmed ALT or AST > 3 × ULN by repeat testing with new sample along with new appearance of fatigue, nausea, vomiting, right upper quadrant pain or tenderness, fever, rash, and/or eosinophilia (> 5% increase from Baseline).
	 Interrupt study drug if confirmed ALT or AST > 5 × ULN by repeat testing with new sample for more than 2 weeks.
	 If ALT or AST > 8 × ULN, interrupt study drug immediately, confirm by repeat testing with a new sample, and contact the TA MD.
	Subjects with HBc Ab+ (irrespective of hepatitis B surface antibody status) and negative HBV DNA PCR testing at Screening who develop the following laboratory findings should have HBV DNA PCR testing performed within 1 week (based on initial elevated value):
	• ALT > 5 × ULN OR
	 ALT or AST > 3 × ULN if an alternative cause is not readily identified.
	 A separate blood sample for HBV DNA PCR testing will be needed at the time of repeat testing for ALT or AST.
	A positive result for HBV DNA PCR testing will require immediate interruption of study drug (unless not acceptable by local practices) and a hepatologist consultation should occur within 1 week for recommendation regarding subsequent treatment.
	Subjects who meet any of the above criteria should be evaluated for an alternative etiology of the ALT or AST elevation and managed as medically appropriate. If applicable, the alternative etiology should be documented in the eCRF. If ALT or AST values return to the normal reference range or its Baseline value, study drug may be restarted. If restarting study drug, documentation should include reason that rechallenge is expected to be safe. If after clinically appropriate evaluation, no alternative etiology for ALT or AST elevation is found or the ALT or AST elevation has not resolved or is not trending down toward normal, the subject should be discontinued from study drug.
	For any confirmed ALT or AST elevations > 3 ULN, complete the appropriate supplemental hepatic eCRF(s).

Laboratory Parameter	Toxicity Management Guideline	
Serum Creatinine	 If serum creatinine is > 1.5 × the Baseline value and > ULN, repeat the test for serum creatinine (with subject in an euvolemic state) to confirm the results. If the results of the repeat testing still meet this criterion, then interrupt study drug and restart study drug once serum creatinine returns to ≤ 1.5 × Baseline value and ≤ ULN. For the above serum creatinine elevation scenarios, complete the supplemental renal 	
	eCRF.	

Elective and Emergency Surgeries

For elective and emergency surgeries the following rules will apply:

- If the subject must undergo emergency surgery, the study drug should be interrupted at the time of the surgery. After emergency surgery, allow reintroduction of study drug once the physician has examined the surgical site and determined that study drug may be safely restarted.
- Elective surgery, and interruption of study drug for such a surgery, will not be allowed until after
 the Week 16 visit has been completed. If the subject undergoes elective surgery, the study drug
 should be interrupted at least 1 week prior to the planned surgery. Allow reintroduction of
 study drug once the physician has examined the surgical site and determined that study drug
 may be safely restarted.

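### The ALT/AST restart sentence in Protocol Table 3 omits the alternative-cause condition, so a resolved but unexplained elevation meets both the restart and the stop sentence

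*Protocol*

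**What the plan says.** Once an interruption criterion in the ALT/AST row of Table 3 is met, the closing paragraph of the row asks for an evaluation for another cause. It then gives two instructions about study drug.

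- **Restart.** "If ALT or AST values return to the normal reference range or its Baseline value, study drug may be restarted". The next sentence adds only a record-keeping duty: "If restarting study drug, documentation should include reason that rechallenge is expected to be safe".
- **Stop.** The subject should come off study drug if, after appropriate evaluation, "no alternative etiology for ALT or AST elevation is found or the ALT or AST elevation has not resolved" or is not moving back toward normal.

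The ANC < 500/µL entry in the same table handles the same decision differently. After recovery, "restarting study drug is allowed if there is an alternative etiology identified", with the same kind of rechallenge documentation, and "Study drug should be discontinued if no alternative etiology can be found".

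Protocol Section 5.5 opens its list with "Subjects must have study drug discontinued immediately if any of the following occur". One item covers laboratory results that meet the Section 6.2 discontinuation criteria or that rule out safe continuation. That item closes by referring to the judgement of the investigator or the sponsor's medical director.

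**The concern.** The restart sentence tests recovery only. The stop sentence tests for a cause as well, and treats the absence of one as sufficient. A subject whose transaminases have returned to normal with no explanation found satisfies both. A site that acts on the restart sentence may re-dose that subject. A site that acts on the stop sentence will not. Both can point to Table 3.

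What is at stake is re-exposure after an unexplained liver-enzyme rise, and uneven handling between sites. Handling also affects how the case is classified: SAP Appendix A counts subjects who developed withdrawal criteria but were not withdrawn, so whether a restarted subject is a protocol deviation depends on which sentence is taken to govern.

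**Working it through.** No arithmetic applies. The check sets the two sentences against each other for every combination of recovery and cause, and then compares the result with the ANC entry.

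**Inputs**

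- Restart rule (Table 3, ALT/AST): values back to normal or Baseline. No condition on cause.
- Stop rule (Table 3, ALT/AST): no cause found, *or* not resolved, *or* not trending down. Any one is enough.
- Rechallenge documentation: a reason to expect safety. It does not have to be an identified cause.

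**As written**

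| Elevation | Alternative cause | Restart sentence | Stop sentence | Result |
|---|---|---|---|---|
| Resolved | Found | Permits | Not met | Restart allowed |
| Resolved | Not found | Permits | Met | Both apply |
| Not resolved | Found | Does not permit | Met on the literal *or* | Stop |
| Not resolved | Not found | Does not permit | Met | Stop |

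One of the four combinations draws both instructions. This counts logical cases and says nothing about frequency.

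**With the cause condition added to the restart sentence**

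The restart rule becomes: resolved *and* cause found. The second row then reads: restart not permitted, stop met, result stop. The other three rows do not change. Conflicting combinations: 0 of 4.

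**Comparison with ANC < 500/µL**

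Restart there needs recovery and a cause, and the absence of a cause leads to discontinuation. A resolved, unexplained case gives one answer: stop. That entry asks for the rechallenge rationale in addition to a cause, so the table does not treat the rationale as a substitute for one.

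**Is the text current?**

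Yes. The summary of changes (Protocol Appendix E) records an edit to the transaminase guidance only for the > 8 × ULN rule. Nothing is redacted or missing in the paragraph.

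**The case against.** The best reply is that an ordinary reader would not be misled. The restart sentence is permissive (*may*) and the stop sentence is directive (*should*). A general permission followed shortly afterwards by a specific exclusion is normally read as limited by it. The paragraph also begins by requiring a search for a cause in every triggered subject. This largely stands, and it is why the paragraph as a whole favours discontinuation. But no sentence states the order of priority, and the permission is complete on its own terms.

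Timing narrows the problem further. The stop sentence applies once evaluation is done. If evaluation ends without a cause before the enzymes recover, the stop comes first and restart never arises. The overlap matters when values normalise while evaluation is still open, or when the site has held drug without stopping it. That is a real limit, but the restart sentence does not wait for evaluation to finish, so the case remains possible.

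There are also safeguards. Confirmed elevations above 3 × ULN require the supplemental hepatic eCRF, hepatic disorder is an adverse event of special interest, and the DMC reviews laboratory values. Above 8 × ULN the site must "interrupt study drug immediately, confirm by repeat testing with a new sample, and contact the TA MD". A positive HBV DNA result requires interruption (unless local practice does not accept it) and a hepatologist's recommendation. A reader might infer that re-dosing would go unseen by the sponsor; the documents do not support that. However, apart from the hepatologist's advice in the HBV case, where the result itself suggests a cause, these measures report or review events, and the row does not make sponsor approval a condition of restart.

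A reader might also infer that Section 5.5 turns the stop sentence into an absolute mandate, so that the restart sentence authorises a breach of it. That is too strong. The reference to the judgement of the investigator or medical director may qualify the whole item or only its second limb, and Table 3 is framed as guidelines using *should*. Section 5.5 supports stopping without settling the matter beyond argument.

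**Conclusion.** The point holds as a minor participant-safety wording correction. For a resolved ALT or AST elevation with no cause found, Table 3 gives both a permission to restart and a direction to stop, with no stated priority. The better reading is to stop. It rests on the directive wording of the stop sentence, on Section 5.5, and on the parallel ANC entry.

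The size is one logical case in four. The documents give no rate for such elevations, so no expected number of subjects is stated.

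A reader might infer that the trial's results are at risk. The documents do not show that. SAP Section 8.0 counts only antibiotic initiation for HS-related infection and discontinuation for lack of efficacy as intercurrent events, so a hepatic discontinuation does not by itself make a subject a non-responder. Protocol Section 5.6 asks for continued visits after study drug is stopped. No effect on any efficacy analysis is shown.

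The conclusion assumes that the *or* in the stop sentence is meant literally for the no-cause limb. If the sponsor intended to allow restart after full recovery without a cause, the stop sentence is the one that is wrong, and the text still needs correcting.

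**What to change.** In the ALT/AST row of Table 3, insert after the recovery condition of the restart sentence: *and an alternative etiology has been identified*. Keep the rechallenge documentation requirement, the stop sentence and Section 5.5 as they are. The row then matches the ANC < 500/µL entry.

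The cost is one clause at the next amendment, with no new procedures and no SAP change. The downside is slightly less investigator discretion in resolved, unexplained cases, most of which the stop sentence already withholds.

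Two limits should be noted. The change does not settle how the stop sentence treats an elevation that is improving with a known cause but has not yet resolved; that question is separate. And if restart without a cause is what the sponsor wants, the alternative repair is to limit the stop sentence to elevations that have not resolved.
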